2.1 Definitions

2.1.1 Study drug and study treatment

Study drug refers to LDE225 and INC424. Study treatment refers to LDE225 XXmg + INC424 XXmg, for example, LDE225 400mg + INC424 10mg.

2.1.2 Monotherapy vs. combination studies

This is a combination study.

The *combination therapy* administered is LDE225 jointly with the study treatment partner INC424.

2.1.3 Date of first administration of study treatment

The date of first administration of study drug is derived as the first date when a nonzero dose of study treatment was administered and recorded on LDE225 or INC424 DAR eCRF. The date of first administration of study treatment will also be referred as the *start date of study treatment*.

2.1.4 Date of last administration of study treatment

The date of last administration of study drug is defined as the last date when a nonzero dose of study drug was administered and recorded on LDE225 or INC424 DAR eCRF. This date of last administration of study treatment will also be referred as the *last date of study treatment*.

2.1.5 Study day

The term assessment will be used to represent an evaluation, a measurement or an event (e.g. AE onset, laboratory abnormality occurrence, tumor assessment, disease progression, etc)

The study day *for all assessments* (efficacy, safety, QoL, etc.) will be calculated as follows:

Study day = date of assessment – start date of study treatment + 1
if date of assessment is after the start date of study treatment.

Study day = date of assessment – start date of study treatment
if date of assessment is before the start date of study treatment.

For any assessment or events such as baseline disease characteristics or medical history (e.g., time since diagnosis of disease) that is supposed to occur prior to the start date of the study treatment, study day will be negative. There is no Day 0 defined.

2.1.6 Baseline

Baseline values for safety and non-safety evaluations are defined as below unless specified otherwise in the RAP.

For *safety evaluations* (e.g. laboratory and vital signs), the last assessment available before or on the start date of study treatment (only if such assessment is pre-dose) is taken as a “baseline” assessment, except for the definition of ECG baseline (see Section 3.8.4.1). If there are multiple assessments on the same day and it is not possible to distinguish the last one for baseline assessment, then the average of these multiple assessments will be used with exception that if those assessments are from both central lab and local lab, the assessment(s) from central lab will be used.

For *efficacy and other non-safety evaluations* (e.g. MRI scan or photograph), the last available assessment before or on the start of study treatment date and is taken as the “baseline” value or “baseline” assessment. Multiple assessments on the same day are not expected.

If patients have no assessments as defined above, the baseline result will be missing.

2.1.7 On-treatment assessment or event

The overall observation period will be divided into three mutually exclusive segments:

pre-treatment period: from day of patient’s informed consent to the prior start date of study treatment

on-treatment period: from day of start of study treatment to 30 days following the last date of study treatment:

[Start date of study treatment; last date of study treatment + 30 days].

post-treatment period: starting at day 31 after last dose of study medication.

On-treatment assessment is defined as any assessment reported in the on-treatment period.

2.1.8 Last contact date

The last contact date will be derived for patients not known to have died at the analysis cut-off using the latest complete date among the following:

- All assessment dates (e.g. vital signs assessment, performance status assessment, and also assessment date in third-party data such as tumor imaging, central laboratory, ECG etc.)
- Medication dates including study medication, concomitant medications, antineoplastic therapies administered after study treatment discontinuation.
- Adverse events dates including the start and stop date of AEs
- Date of treatment assignment or start/last date of study treatment
- Date of discontinuation from ‘End of Treatment’ eCRF

Only dates associated with patient visits or actual examinations of the patient will be used in the derivation. Dates associated with a technical operation unrelated to patient status such as the date a blood sample was processed, will not be used. An imputed partial date will not be used to derive the last contact date. The assessment dates after the cutoff date will not be applied to derive the last contact date.

2.1.9 Screening failure

The purpose of providing screening failures is to ensure that there was no bias in choosing patients who were enrolled into the study.

Screening failures are potential subjects who did not meet one or more screening criteria required for participation into the study. These patients are never treated.

Patients who met inclusion and exclusion criteria but they were never treated will be considered enrolled and will be listed separately.

2.1.10 Month

A month will be calculated as $(365.25 / 12) = 30.4375$ days. If duration is to be reported in months, duration in days will be divided by 30.4375.

2.1.11 Handling of missing values

2.1.11.1 Adverse events data imputation

Date imputation is the creation of a new, complete date from a partial one according to an agreed and acceptable algorithm.

A partial date is simply an incomplete date e.g.,
ddOCT2001 the days are missing from this DDMMMYYYY date

Partial adverse event start dates, if left partial, would ultimately mean the following

- It would not be possible to place the adverse event in time.
- Therefore the treatment/dosage at the time of the event would be unknown.
- Therefore the event could not be reported/summarized appropriately – if at all.

Therefore it is important to perform date imputation to ensure that as many data events are represented as correctly as possible. Of course partial and/or missing dates should *also* be caught as edit checks and passed back to the investigator for resolution.

There will be no attempt to impute the following:

- Missing AE start dates
- AE start dates missing the year
- Missing AE end dates

Table 2-1 explains the abbreviations used.

Table 2-1 AE/Treatment date abbreviations

	Day	Month	Year
Partial adverse event start date	<not used>	AEM	AEY
Treatment start date (TRTSTD)	<not used>	TRTM	TRTY

Table 2-2 describes the possible combinations and their associated imputations. In the light grey boxes the upper text indicates the imputation (NC, A, B, C, etc.) and the lower text the relationship of the AE start date to the treatment start date (TRTSTD).

Table 2-2 Imputation algorithm

	AEM	MISSING	AEM < TRTM	AEM = TRTM	AEM > TRTM
AEY MISSING	NC	NC	NC	NC	NC
	Uncertain	Uncertain	Uncertain	Uncertain	Uncertain
AEY < TRTY	(D)	(C)	(C)	(C)	(C)
	Before TRTSTD	Before TRTSTD	Before TRTSTD	Before TRTSTD	Before TRTSTD
AEY = TRTY	(B)	(C)	(B)	(B)	(A)
	Uncertain	Before TRTSTD	Uncertain	Uncertain	After TRTSTD
AEY > TRTY	(E)	(A)	(A)	(A)	(A)
	After TRTSTD	After TRTSTD	After TRTSTD	After TRTSTD	After TRTSTD

The legend to the above table is shown in Table 2-3.

Table 2-3 Imputation algorithm legends

Relationship	
Before TRTSTD	Indicates AE start date prior to Treatment Start Date
After TRTSTD	Indicates AE start date after Treatment Start Date
Uncertain	Insufficient to determine the relationship of AE start date to Treatment Start Date
Imputation calculation	
NC / Blank	No convention/imputation
(A)	01MONYYYY
(B)	TRTSTD+1
(C)	15MONYYYY
(D)	01JULYYYY
(E)	01JANYYYY

Few examples are shown in Table 2-4.

Table 2-4 Example scenarios

Partial AE start date	Treatment start date	Relationship with TRTSTD	Imputation calculation	Imputed date
12mmyyyy	20OCT2001	Uncertain	NC	<blank>
ddmmm2000	20OCT2001	Before	(D)	01JUL2000
ddmmm2002	20OCT2001	After	(E)	01JAN2002
ddmmm2001	20OCT2001	Uncertain	(B)	21OCT2001
ddSEP2001	20OCT2001	Before	(C)	15SEP2001
ddOCT2001	20OCT2001	Uncertain	(B)	21OCT2001
ddNOV2001	20OCT2001	After	(A)	01NOV2001

2.1.11.2 Incomplete date of concomitant medication Diagnosis

The imputation of the start date of concomitant medication will follow the same convention for AE date. Partial concomitant medication end date will not be imputed.

2.1.11.3 Incomplete date of initial diagnosis of myeloproliferative disorder

For incomplete date of initial diagnosis of myeloproliferative disorder, missing day is defaulted to 15 and missing month and day is defaulted to Jan 01 respectively.

2.1.11.4 Incomplete date of anti-neoplastic therapies (myeloproliferative neoplasm directed therapy)

Prior therapies

- Start date:** The same rule which is applied to the imputation of AE/concomitant medication start date will be used with the exception that: for scenario (B) will be replaced to be start date treatment-1.

- End date:**

- Imputed date = min(reference end date, DEC 31) , if month and day are missing.

- Imputed date = min(reference end date, last day of the Month) , if day is missing.

- Reference end date will be the start date of treatment.

- If the end date is not missing and the imputed start date is after the end date, use the end date as the imputed start date.

- If both the start date and the end date are imputed and if the imputed start date is after the imputed end date, use the imputed end date as the imputation for the start date

Post therapies

- Start date:**

- If Day is missing, then impute to the max (reference start date, first day of the month).

- Day and month are missing then impute to the max(reference start date, Jan 1)

- Reference start date will be last date of study treatment administration + 1.

- End date:** No imputation

2.1.11.5 Incomplete dates for last contact or death

All dates must be completed with day, month and year. If the day is missing, the 1st of the month will be used for incomplete death dates or dates of last contact.

2.1.11.6 Incomplete dates for last treatment administration

Scenario 1: If the last treatment administration date is completely missing and there is no EOT page and no death date:

The patient should be treated as on-going and use the cutoff date as the last dosing date up to date.

Scenario 2: If the last treatment administration date is completely or partially missing and there is either EOT page or death date available:

If only Year is available and $\text{Year} < \text{Year of min}(\text{EOT date, death date})$;

Imputed date= Dec31yyyy

If both Year and Month are available, $\text{Year} = \text{Year of min}(\text{EOT date, death date})$ and $\text{Month} < \text{the month of min}(\text{EOT date, death date})$;

Imputed date= last day of the Month

All other cases imputed date= $\text{min}(\text{EOT date, death date})$.

The imputed date will be compared with start date of treatment. If the imputed date is $<$ start date of treatment, set the last treatment administration date to be the treatment start date; otherwise use the imputed date.

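### Two SAP partial-date rules can return dates that the record itself rules out: a last dose moved across a year boundary to the EOT or death date, and a start date after a known pre-dose end date

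*SAP*

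**What the plan says.** **Last dose (SAP 2.1.11.6, Scenario 2).** The reference date is the earlier of the EOT date and the death date.

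- Year branch ("If only Year is available and"): if that year is before the reference year, impute 31 December.
- Month branch ("If both Year and Month are available"): if the year equals the reference year and the month is earlier, impute the last day of the month.
- Fallback ("All other cases imputed date"): impute the reference date.

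One check follows: "The imputed date will be compared with start date of treatment". It only stops the imputed date from falling before treatment start.

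**AE and medication start (SAP 2.1.11.1, Tables 2-2 to 2-4, and 2.1.11.2).** Rule (B) applies when the partial start is in the treatment-start month, or in the treatment-start year with the month missing. It returns treatment start plus one day. The end date is not an input; it is mentioned only among the items not imputed ("Missing AE end dates"). For medications, "The imputation of the start date of concomitant medication will follow the same convention for AE date".

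**Prior anti-neoplastic therapy (SAP 2.1.11.4).** Here rule (B) becomes treatment start minus one day, and a guard is added: "If the end date is not missing and the imputed start date is after the end date, use the end date" as the start.

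**The concern.** An imputed date should agree with the parts of the date that are known. Neither rule ensures this.

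The last-dose date feeds duration of exposure (SAP 3.3.1), dose intensity and relative dose intensity (3.3.4), and the on-treatment period of last dose plus 30 days (2.1.7). That period governs the laboratory, ECG and PRO summaries. The date also sets the reference start for imputing partial dates of post-study therapies (2.1.11.4).

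The start date decides whether an AE meets the lower bound for the summaries, study day 1 (3.8.1.3). It also decides whether a medication is summarised as concomitant or only listed as prior (3.4).

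The inputs can arise. The last date is that of the last nonzero dose (2.1.4), and SAP 3.3.5 provides for a final zero dose before permanent discontinuation, so EOT can fall after the last dose. AEs are captured from consent (Protocol 8.1.1), screening lasts up to 21 days (Protocol 7.1.1), and medications from the 30 days before first dose are recorded (Protocol 7.1.1.2).

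**Working it through.** **Reproducing the plan's own figures.** Coding SAP Tables 2-2 and 2-3 literally reproduces all seven rows of Table 2-4. With treatment start 20OCT2001, both the partial start ddOCT2001 and the year 2001 alone return 21OCT2001 under rule (B).

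The dates below are test inputs, not trial data, except that 20OCT2001 is taken from Table 2-4.

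**Last-dose rule.** Days too late = imputed date minus the latest date the record allows.

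| Known part | EOT | Branch | Imputed | Latest possible | Days too late |
|---|---|---|---|---|---|
| 2014 | 12JAN2015 | year | 31DEC2014 | 31DEC2014 | 0 |
| DEC2014 | 12JAN2015 | fallback | 12JAN2015 | 31DEC2014 | 12 |
| NOV2015 | 20DEC2015 | month | 30NOV2015 | 30NOV2015 | 0 |
| DEC2015 | 20DEC2015 | fallback | 20DEC2015 | 20DEC2015 | 0 |
| NOV2015 | 12JAN2016 | fallback | 12JAN2016 | 30NOV2015 | 43 |

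The fallback is sound when EOT lies in the recorded month (fourth row). It fails only when month and year are known and the reference date is in a later year (second and fifth rows). The first two rows show that knowing the month gives a worse answer than not knowing it.

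For a December last dose, an EOT of 1 January gives 1 day too late and an EOT of 31 January gives 31 days, so the range is 1 to 31 days.

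**Effect on exposure.** Assume treatment start on 1 June 2014 and EOT on 12 January 2016. Duration = last dose - first dose + 1.

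- Imputed last dose 12JAN2016: 591 days.
- Last dose in December 2015: at most 579 days. 579/591 = 0.980, so dose intensity is understated by at least 2.0%.
- Last dose in November 2015: at most 548 days. 548/591 = 0.927, so dose intensity is understated by at least 7.3%.

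This holds the cumulative dose fixed. Relative dose intensity falls by the same factor, because the planned dose accumulates over the same lengthened duration.

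**Start-date rule**, with treatment start 20OCT2001.

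- AE with start ddOCT2001 and end 12OCT2001: imputed start 21OCT2001. Study day = 21 - 20 + 1 = 2, and the start is 21 - 12 = 9 days after the event's own end. The AE meets the day-1 criterion and is summarised.
- Medication with start year 2001 only and end 30SEP2001: imputed start 21OCT2001, 21 days after its end. It is summarised as concomitant, although SAP 3.4 says that medications starting and ending before treatment are only listed.
- Prior-therapy rule on ddOCT2001 with end 12OCT2001: imputed 19OCT2001, then capped at 12OCT2001. The SAP already contains the logic that the AE and medication rules lack.

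**The case against.** The strongest reply is that these cases will be rare and short. SAP 2.1.11.1 says partial dates should be caught by edit checks and returned to the investigator, and Protocol 9.3 and 9.4 provide automatic validation and queries. Protocol Table 7-1 labels the EOT column as the date of last dose, and the protocol summary asks for the EOT visit as soon as possible after discontinuation. Protocol 7.1.3 requires discontinuation after an interruption of more than 21 days, with an exception for patients deriving benefit. If EOT sits at the last dose, falling back to it is a reasonable default. For AEs, treating an uncertain start as on-treatment is an openly stated, conservative choice, and the event must begin and end within a short screening window.

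Most of this stands, as an argument about frequency and size. It does not repair the rules, which exist for queries that stay unresolved. The conservative default explains rule (B) when timing is uncertain. It does not explain overriding an end date that settles the question.

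A reader might infer that errors of two to three months are typical, for example a November last dose with a late-January EOT. The arithmetic allows that, but the intended EOT timing makes it atypical. A reader might also infer that the AE start date alone decides tabulation. It does not: SAP 3.8.1.3 has an upper bound of 30 days after end of treatment, and all AEs are listed in any case.

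**Conclusion.** Both defects follow from the literal text, and both are minor. The last-dose fault needs month and year known, with EOT or death in a later calendar year; for December with a January EOT the error is 1 to 31 days, measured from the latest date the record allows. The start-date fault needs a partial start under rule (B) and a known end date before dosing; every such record is misclassified.

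The documents give no frequency, so the total effect cannot be estimated. The query step and EOT timing suggest few cases. The conclusion rests on reading the branches as written and on some partial dates remaining after queries.

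A reader might infer that the efficacy result or the overall safety picture is at risk. The documents do not support that. Spleen response (SAP 3.5.2.1 and 3.5.3) is not derived from these imputed dates, and the affected tables are descriptive summaries in which a rare imputed date moves one patient's record.

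**What to change.** 1. **SAP 2.1.11.6:** apply the last-day-of-month rule whenever the known year and month, taken together, are earlier than the year and month of min(EOT date, death date). DEC2014 with EOT 12JAN2015 then gives 31DEC2014, and NOV2015 with EOT 12JAN2016 gives 30NOV2015. Same-year cases do not change.
2. **SAP 2.1.11.1 and 2.1.11.2:** add the guard from 2.1.11.4, so that if a known end date precedes the imputed start, the end date becomes the start. The AE example then starts on 12OCT2001 and the medication on 30SEP2001, both before dosing. Rule (B) can stay as it is where the end date leaves the timing open; the minus-one-day version for prior therapy need not be copied.

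The guard needs a complete end date. An incomplete one stays outside it, since the SAP does not impute end dates for AEs or medications.

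The cost is two SAP lines and a small programming change. No new data are needed.

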2.2 Analysis sets

This section defines standard analysis sets and their use for statistical analyses.

2.2.1 Full analysis set (FAS)

Phase Ib and Phase II:

The Full Analysis Set (FAS) comprises all patients in Phase Ib and Phase II who received at least one dose of LDE225 and/or INC424.

Patients will be classified according to the assigned treatment combination. Unless otherwise specified the FAS will be the default analysis set used for all analyses.

2.2.2 Safety analysis set (SAS)

Phase Ib and Phase II:

The Safety Analysis Set (SAS) includes all patients in Phase Ib and Phase II who received at least one dose of LDE225 and/or INC424, and had at least one valid post-baseline safety assessment.

Patients will be analyzed according to the study treatment (regimen) they actually received, where treatment received for each drug is defined as (i) the treatment assigned if it was received at least once, or else (ii) the first treatment received when starting study medication. Each patient will be classified into and analyzed consistently within one (and only one) treatment group.

2.2.3 Dose Determining set (DDS)

The dose Determining set (DDS) consists of all patients from the safety set of Phase Ib who either meet the following minimum exposure criterion and have sufficient safety evaluations (as determined by the investigators and Novartis), or discontinue earlier due to DLT. This constitutes an evaluable patient for the determination of the MTD.

A patient is considered to have met the minimum exposure criterion at treatment group if the patient receives at least 75% of the planned doses of LDE225 and INC424 within 6 weeks (42 days) following the first dose (i.e., no more than 10 missed doses of LDE225 and no more than 20 missed doses of INC424 in 6 weeks are permitted). Patients who do not meet these minimum exposure and safety evaluation requirements will be regarded as ineligible for inclusion into the DDS. Patients in the DDS will be identified before database lock.

2.2.4 Pharmacokinetic analysis set (PAS)

Phase Ib and Phase II:

The pharmacokinetic analysis set (PAS) consists of all patients in Phase Ib and Phase II who receive at least one (full or partial) dose of LDE225 and/or INC424 and provide at least one evaluable PK blood sample for LDE225 and/or INC424.

2.2.5 Biomarker analysis set (BAS)

The Biomarker Analysis Set (BAS) consists of all patients in Phase Ib and Phase II who receive at least one (full or partial) dose of LDE225 and/or INC424 and provided at least one evaluable biomarker sample.

2.3 Protocol deviations

2.3.1 Anti-neoplastic therapy administered after start of study treatment

Patients who take any anti-neoplastic therapy before discontinuing study treatment (i.e. anti-neoplastic therapy other than study treatment) will be identified as protocol deviations. Their efficacy data will be censored so that response assessments made after the intake of an anti-neoplastic drug will not be included in analyses.

3 Data analysis methods

3.1 General presentation of descriptive summaries and listings

Categorical data or qualitative characteristics of a subject (e.g., gender, race, subject disposition, etc.) will be summarized by frequency count (number of subjects) and percentages. Percentages will be calculated using the number of subjects in the relevant population or subgroup as the denominator.

Continuous data (e.g., age, body weight, etc.) will be summarized by appropriate descriptive statistics (mean, standard deviation, median, minimum, and maximum).

Summary of data will be presented by patient group, treatment and overall.

3.1.1 Multiple assessments within post-baseline visits

If there are multiple measurements/samples within the same post-baseline visit, the last measurement/sample within the visit (sorted by date and as available by time or repeat measurements) will be used in the analysis by visit or overall.

For any analyses regarding outlier or abnormal assessments, all post-baseline values will be included (scheduled, unscheduled, repeat). For any other analyses, only scheduled visits will be included. This applies to quantitative and qualitative variables.

For composite assessments these rules apply for the complete sample (e.g. bone marrow differential counts, differential blood counts). It is not allowed to mix these variables across samples.

3.1.2 Center pooling

All study centers will be combined for the analysis unless otherwise specified. In general, no center effect will be assessed due to expected small size of centers.

